### 10.8. Recording of Concomitant Medications

All changes in prior and new prescription and non-prescription medications (including i.v. immunoglobulins, blood products, use of vitamins, supplements and herbal remedies) from the start of screening through the final study visit are to be recorded. For each change in prior medication and new medication the following will be recorded:

- Name of the medication
- Total daily dose
- Route of administration
- The start and stop dates
- The indication for use
  - If a product is being taken for the prevention of a condition, “prophylaxis for” or “prevention of” should be included in the description of indication
  - If a product is being taken for an active condition, a corresponding medical condition must be included in the medical history

### 10.9. Compliance

This study is to be conducted according to:

- United States (U.S.) and international standards of Good Clinical Practices (GCP) as defined in the U.S. Food and Drug Administration (FDA) Code of Federal Regulations (CFR), and International Conference on Harmonization (ICH) guidances,
- Applicable government regulations,

- Institutional Review Board(s) (IRB)/Independent Ethics Committee(s) (IEC), and
- Institutional (study site) research policies and procedures.

The Principal Investigator and the study personnel will verify patient compliance with the study requirements, procedures and schedule of events. The Principal Investigator or physician Sub-Investigator (listed on Form FDA 1572) will be present for the initial dose administration of Adagen® during the Lead-In phase and EZN-2279 (Week T-1) and for the post-dose monitoring and evaluation for all patients. The Principal Investigator or physician sub-investigator will be available and accessible at all other times throughout the study for the management of the patients enrolled in this clinical trial. Non-compliance with any study evaluations/procedures will be documented in the patient's source documents and case report forms (CRFs).

## 11. SCHEDULE OF STUDY PROCEDURES

Study activities are listed in Appendix 1.

### 11.1. Screening

Patients who fulfill all of the inclusion criteria and none of the exclusion criteria may be entered into the study.

The following evaluations are to be performed within 28 days before start of the Adagen® Lead-in period unless otherwise indicated.

- Informed assent/consent
- Obtain patient history and baseline characteristics
  - Demographics
  - Disease background and history
  - Assessment of AEs/toxicities the patient has experienced while on Adagen® treatment
  - Assessment of infectious complications and hospitalizations within the past 12 months
  - Medical history
  - Medication history
- Physical examination
- Vital signs
- Height and weight for growth assessment
- Performance status score
- Urine or serum pregnancy test for females of childbearing potential must be performed within 7-days before starting Adagen® Lead-in.
- Safety Lab
  - Hematology
  - Serum chemistry
  - Urinalysis
- Immunogenicity - Adagen® antibody titers (i.e., neutralizing and binding antibodies) and anti-PEG antibodies

Patients passing screening assessment will enter the Adagen Lead-in phase of the study.

For patients currently maintained with Adagen® on a 1 time per week dosage regimen, the following additional laboratory assessments will be performed to determine whether an Adagen® dosage adjustment when entering the Adagen® Lead-in phase is required:

- Total erythrocyte dAXP from a trough blood sample
- Trough plasma ADA activity

## 11.2. Adagen® Lead -in

### 11.2.1. Adagen® Dosage and Schedule Adjustments

Patients entering the Lead-in phase will have Adagen® dose/dose schedule changes implemented prior to the first Adagen lead-in dose as described below:

- Patients on once weekly Adagen® dosing and meet entry criteria for dAXP level and ADA activity – these patients will enter Adagen® Lead-in on the dose and regimen he/she was taking prior to study entry
- Patients on once weekly Adagen® dosing and do not meet entry criteria for dAXP levels and ADA activity – these patients should have his/her dosage adjusted (see Section 10.7.2)
- Patients on two or more weekly doses of Adagen® – these patients will have his/her dose regimen of Adagen® consolidated into a single weekly dose. For example, a patient receiving 20U/kg twice weekly will have his/her dose regimen consolidated to a dose of 40U/kg once weekly.

### 11.2.2. Weekly Adagen Dosing

Patients will have weekly study visits ( $\pm 1$  day). For each visit, the patient will return to the study site have the following procedures performed:

- Adverse event assessment
- Assessment of infectious complications and hospitalizations
- Assessment of concomitant medications and procedures since last study visit
- Trough blood samples will be obtained 15 to 30 minutes prior to Adagen® dosing for:
  - dAXP
  - ADA activity

The patient will receive his/her dose of Adagen®.

Patients will be followed weekly for dAXP and ADA activity.

- If the results of these tests indicate a dAXP level  $\leq 0.02$   $\mu\text{mol/mL}$  and a trough ADA activity level  $\geq 15$   $\mu\text{mol/h/mL}$  for two consecutive weekly measurements and all other section criteria are still met the patient will be able to proceed to the Adagen® Pharmacokinetic assessment (see Section 11.2.3).
- If the dAXP and trough ADA activity levels do not meet protocol selection criteria for two consecutive weeks and the patient is not considered fully detoxified, the patient should have his/her dosage re-adjusted (see Section 10.7.2). This process may be repeated until the patient meets the ADA activity and dAXP levels and is considered fully detoxified for study inclusion.

A schematic diagram of procedures for dose adjustment and consolidation is provided in Appendix 4.

### 11.2.3. Adagen® Pharmacokinetics

#### 11.2.3.1. Day 1

Day 1 is the day of the first administration of Adagen® on study. Prior to administration of Adagen® the following baseline procedures will be performed:

- Update medical history
- Physical examination
- Height and weight for growth assessment

- Performance status
- Vital Signs
- Safety Lab
  - Hematology
  - Chemistry
  - Urinalysis
- Other labs – blood samples will be obtained 15 to 30 minutes prior to dosing for:
  - dAXP
  - Trough ADA activity
  - B-, T-, and NK-lymphocyte subset analysis
  - Quantitative immunoglobulins
  - Adagen® antibody titers (i.e., neutralizing and binding antibodies) and anti-PEG antibodies
- Assessment of concomitant medications and procedures since last study visit

Following completion of the above procedures, the patient will receive Adagen® at his/her current weekly dose administered as a single weekly injection.

#### 11.2.3.2. Days 2 through 8

Blood samples for ADA activity will be obtained at 24, 48, 72, 96, 120, 144, and 168 hours following Day 1 PK dose. All blood samples will be obtained  $\pm$  4 hours of the scheduled collection time. Note: the 168 hour post-dose sample will be obtained immediately prior to the initial dose of EZN-2279.

For patients < 10 years of age, PK sampling will be limited to trough samples and at 48 hours post dose for monitoring of ADA activity and  $C_{max}$  timepoint.

### 11.3. EZN-2279 Study Treatment Period

#### 11.3.1. Day 1 (Week T-1)

Prior to administration of EZN-2279 the following procedures will be performed:

- Physical examination
- Height and weight for growth assessment
- Performance status
- Vital Signs
- Safety Lab
  - Hematology
  - Chemistry
  - Urinalysis
- Other labs – blood samples will be obtained 15 to 30 minutes prior to dosing for:
  - dAXP
  - Trough ADA activity (168 hours following Day 1 Adagen® PK dose)
  - B-, T-, and NK-lymphocyte subset analysis
  - Quantitative immunoglobulins
  - EZN-2279 and Adagen® antibody titers (neutralizing and binding antibodies) and anti-PEG antibodies
- Adverse event assessment
- Assessment of infectious complications and hospitalizations
- Assessment of concomitant medications and procedures since last study visit

Following completion of the above procedures, the patient will receive EZN-2279. The equivalent dose of EZN-2279 will be calculated as described in Sections 7.2.1 and 10.7.1.

#### 11.3.2. Day 8 (Week T-2)

On Day 8 ( $\pm$  1 day) the patient will return to the study site and have the following procedures performed:

- Adverse event assessment
- Assessment of infectious complications and hospitalizations
- Assessment of concomitant medications and procedures since last study visit

The patient will receive his/her dose of EZN-2279 after all procedures have been completed.

#### 11.3.3. Day 15 (Week T-3)

On Day 15 ( $\pm$  1 day) the patient will return to the study site and have the following procedures performed:

- Adverse event assessment
- Assessment of infectious complications and hospitalizations
- Assessment of concomitant medications and procedures since last study visit

Blood samples will be obtained 15 to 30 minutes prior to administration of EZN-2279 for:

- dAXP
- Trough ADA activity
- EZN-2279 antibody titers (i.e., neutralizing and binding antibodies) and anti-PEG antibodies

The patient will receive his/her dose of EZN-2279 after all procedures and laboratory blood draws have been completed.

#### 11.3.4. Day 22 (Week T-4)

On Day 22 ( $\pm$  1 day) the patient will return to the study site and have the following procedures performed:

- Adverse event assessment
- Assessment of infectious complications and hospitalizations
- Assessment of concomitant medications and procedures since last study visit

The patient will receive his/her dose of EZN-2279 after all procedures have been completed.

#### 11.3.5. Day 29 (Week T-5)

On Day 29 ( $\pm$  1 day) the patient will return to the study site and have the following procedures performed:

- Physical examination
- Height and weight for growth assessment
- Performance status
- Vital Signs
- Safety Lab
  - Hematology
  - Chemistry
- Adverse event assessment

- Assessment of infectious complications and hospitalizations
- Assessment of concomitant medications and procedures since last study visit

Blood samples will be obtained 15 to 30 minutes prior to administration of EZN-2279 for:

- dAXP
- Trough ADA activity

The patient will receive his/her dose of EZN-2279 after all procedures and laboratory blood draws have been completed.

#### 11.3.6. Day 36 (Week T-6)

On Day 36 ( $\pm$  1 day) the patient will return to the study site and have the following procedures performed:

- Adverse event assessment
- Assessment of infectious complications and hospitalizations
- Assessment of concomitant medications and procedures since last study visit

The patient will receive his/her dose of EZN-2279 after all procedures and laboratory blood draws have been completed.

#### 11.3.7. Day 43 (Week T-7)

On Day 43 ( $\pm$  1 day) the patient will return to the study site and have the following procedures performed:

- Adverse event assessment
- Assessment of infectious complications and hospitalizations
- Assessment of concomitant medications and procedures since last study visit

Blood samples will be obtained 15 to 30 minutes prior to administration of EZN-2279 for:

- dAXP
- Trough ADA activity

The patient will receive his/her dose of EZN-2279 after all procedures and laboratory blood draws have been completed.

#### 11.3.8. Day 50 (Week T-8)

On Day 50 ( $\pm$  1 day) the patient will return to the study site and have the following procedures performed:

- Adverse event assessment
- Assessment of infectious complications and hospitalizations
- Assessment of concomitant medications and procedures since last study visit

Blood samples will be obtained 15 to 30 minutes prior to administration of EZN-2279 for:

- dAXP
- Trough ADA activity

The patient will receive his/her dose of EZN-2279 after all procedures and laboratory blood draws have been completed.

### 11.3.8.1. EZN-2279 Dose Evaluation for Adjustment

The results from trough ADA activity and dAXP will be reviewed to assess whether patients have a dAXP level  $\leq 0.02$   $\mu\text{mol/mL}$  and a trough ADA activity level  $\geq 15$   $\mu\text{mol/h/mL}$ .

Based upon this review:

- If the Week T-7 and T-8 values for ADA activity and dAXP levels meet the established values, the patient will proceed to Day 57 (Week T-9) and begin full PK sampling
- If the Week T-7 and T-8 values for ADA activity and dAXP levels **DO NOT** meet the established values and the patient is not considered fully detoxified:
  - The patient will have his/her dosage of EZN-2279 adjusted. Dose adjustments will be based upon dAXP and ADA values and agreed upon by the PI, Sponsor and Lead PI
  - Return to Week T-5 (Section 11.3.5) and continue through weekly dosing for 4 weeks (T-5 through T-8) and be re-assessed as described in this section

### 11.3.9. Day 57 (Week T-9)

On Day 57 ( $\pm 1$  day) the patient will return to the study site and have the following procedures performed:

- Physical examination
- Height and weight for growth assessment
- Performance status
- Vital Signs
- Safety Lab
  - Hematology
  - Chemistry
- Adverse event assessment
- Assessment of infectious complications and hospitalizations
- Assessment of concomitant medications and procedures since last study visit

Blood samples will be obtained 15 to 30 minutes prior to administration of EZN-2279 for:

- dAXP
- Trough ADA activity
- B-, T-, and NK-lymphocyte subset analysis
- Quantitative immunoglobulins

The patient will receive his/her dose of EZN-2279 after all procedures and laboratory blood draws have been completed.

This is the first day of the full PK sampling for EZN-2279. Note: If the dose or schedule of EZN-2279 is altered, the full PK profile should be repeated not earlier than 9 weeks after adjustment of the dose/schedule of EZN-2279.

### 11.3.10. Days 58 through 63 (Week T-9)

The patient will return to the study site each day for blood sampling (only for patients  $\geq 10$  years of age). Blood samples for ADA activity will be obtained at 24, 48, 72, 96, 120, 144, and 168 hours following Day 29 dose. All blood samples will be obtained  $\pm 4$  hours of the scheduled collection time. Note: the 168 hour post-dose sample will be obtained immediately prior to the Week T-10 dose of EZN-2279.

For patients < 10 years of age, PK sampling will be limited to trough samples and at 48 hours post dose for monitoring of ADA activity and Cmax timepoint.

#### 11.3.11. Day 64 (Week T-10)

On Day 64 ( $\pm$  1 day) the patient will return to the study site and have the following procedures performed:

- Adverse event assessment
- Assessment of infectious complications and hospitalizations
- Assessment of concomitant medications and procedures since last study visit

Blood samples will be obtained 15 to 30 minutes prior to administration of EZN-2279 for:

- dAXP
- Trough ADA activity (168 hours following Day 57 EZN-2279 dose)
- EZN-2279 antibody titers (i.e., neutralizing and binding antibodies) and anti-PEG antibodies

The patient will receive his/her dose of EZN-2279 after all procedures and laboratory blood draws have been completed.

#### 11.3.12. Day 71 (Week T-11)

On Day 71 ( $\pm$  1 day) the patient will receive EZN-2279 at a dose of 0.2 mg/kg and have the following procedures performed:

- Adverse event assessment
- Assessment of infectious complications and hospitalizations
- Assessment of concomitant medications and procedures since last study visit

Blood samples will be obtained 15 to 30 minutes prior to administration of EZN-2279 for:

- dAXP
- Trough ADA activity

The patient will receive his/her dose of EZN-2279 after all procedures and laboratory blood draws have been completed.

If the patient will self-administer the Week T-12 dose of EZN-2279, the dose will be dispensed with a dosing diary card and administration instructions.

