#### 10.7.1.2. EZN-2279

EZN-2279 will be administered starting after completion of the Adagen® Lead-in phase. Patients will be transitioned to receive an equivalent dose of EZN-2279 as a weekly i.m. injection. Based upon 1 mg EZN-2279 containing ADA enzymatic activity of 150 U of Adagen®, the equivalent dose of EZN-2279 will be calculated as follows:

$$\text{Adagen® dose (U/kg)} \times 1\text{mg EZN-2279}/150\text{U Adagen®} = \text{EZN-2279 dose (mg/kg)}$$

For example, for a 50 kg patient on a dose of 30 U/kg of Adagen®:

$$\text{Adagen® 30 U/kg} \times \frac{1 \text{ mg EZN-2279}}{150 \text{ U Adagen®}} = 0.2 \text{ mg/kg EZN-2279}$$

$$50 \text{ kg} \times 0.2\text{mg/kg} \times 1 \text{ mL}/1.6 \text{ mg} = 6.25 \text{ mL (10 mg)}$$

The date and time of each dose administered will be recorded.

All patients will be observed for at least 1 hour after administration of EZN-2279 for doses administered at the study site through study Week T-9.

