#### 10.7.2. Dose Adjustments

Adjustments of the dose and/or schedule of EZN-2279 or Adagen® may be required if a patient's trough plasma ADA activity is less than 15 µmol/h/mL and/or the trough dAXP level is greater than 0.02 µmol/mL for two or more consecutive assessments and compliance with the study drug regimen is confirmed and the patient is not considered fully detoxified. The Investigator, the sponsor, and Lead PI must agree upon all modifications in the dosing regimen for each patient before any changes are instituted.

The dose of Adagen® should not be adjusted more than once every 2 weeks and the dose EZN-2279 should not be adjusted more than once every 4 weeks to allow the effect of these changes on trough level of ADA to be manifested.

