#### 11.3.13. Day 78 (Week T-12)

On Day 78 ( $\pm$  1 day) the patient will receive his/her dose of EZN-2279. The dose may be given at the study site or self-administered by the patient.

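### The Week T-11 visit text orders a fixed 0.2 mg/kg of EZN-2279, contradicting the individual dose rule and a later sentence in the same section

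*Protocol*

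**What the plan says.** The governing rule is in Protocol Sections 7.2.1 and 10.7.1.2. "Patients will be transitioned to receive an equivalent dose of EZN-2279 as a weekly i.m. injection", where 1 mg of EZN-2279 counts as 150 U of Adagen. Section 11.3.1 applies it at the first dose: "The equivalent dose of EZN-2279 will be calculated as described in Sections 7.2.1 and 10.7.1".

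The dose can then be changed patient by patient. Section 11.3.8.1 provides, when the T-7 and T-8 values fall short and the patient is not considered fully detoxified: "The patient will have his/her dosage of EZN-2279 adjusted". Section 10.7.2 limits EZN-2279 adjustments to one every 4 weeks. It also requires that the investigator, the sponsor and the lead investigator "must agree upon all modifications in the dosing regimen for each patient before any changes are instituted".

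Section 11.3.12 (Day 71, Week T-11) opens differently: "the patient will receive EZN-2279 at a dose of 0.2 mg/kg". Further down, the same section says "The patient will receive his/her dose of EZN-2279 after all procedures and laboratory blood draws have been completed". It then turns to home dosing: "If the patient will self-administer the Week T-12 dose of EZN-2279, the dose will be dispensed with a dosing diary card". The next visit, Section 11.3.13, returns to the usual form: "the patient will receive his/her dose of EZN-2279".

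The SAP is silent. Its activity table marks an EZN-2279 administration at T-11 without a dose, and SAP Section 3.4 records no changes to design or procedures.

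**The concern.** A site coordinator works from the visit section, and the first dosing statement there is an unconditional number. For any patient whose current dose is not 0.2 mg/kg, the site cannot satisfy both sentences. If it follows the first, the patient gets an unplanned dose of an investigational enzyme that had no prior clinical studies (Section 5.3.2), after being detoxified on an individual dose. That change would arise outside the adjustment criteria and agreement in Section 10.7.2. Going to 0.2 mg/kg at T-11 and back at T-12 would also break the 4-week limit.

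Whichever sentence is followed, the site departs from the other. Section 14.1.2 requires every departure to be recorded, and departures in study drug administration to be notified to the IRB in writing.

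The T-12 home dose is dispensed at this same visit. That is the one point in the text where a misreading could be repeated without supervision.

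**Working it through.** **1. Is T-11 the only exception?** Going through Sections 11.3.1 to 11.3.22, T-1 uses the calculated equivalent dose, and T-2 to T-10 and T-12 to T-21 all refer to the patient's own dose. Only the opening sentence for T-11 names a fixed amount. No rationale for a fixed T-11 dose appears in either document.

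**2. Reproduce the protocol's worked example (Section 10.7.1.2).** A 50 kg patient on 30 U/kg:
- 30 / 150 = 0.2 mg/kg
- 50 × 0.2 = 10 mg
- 10 / 1.6 mg/mL = 6.25 mL

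These match the protocol exactly. The T-11 figure equals this example. That it was carried over from there is an inference.

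**3. Size of the dose error.**
- 30 U/kg (Section 10.7.1 examples): 0.200 mg/kg, no change.
- 40 U/kg (consolidation example, Section 11.2.1): 40 / 150 = 0.267 mg/kg. (0.200 − 0.267) / 0.267 = −25%.
- 20 U/kg once weekly (my assumption, to show the other direction): 20 / 150 = 0.133 mg/kg. 0.200 / 0.133 − 1 = +50%.

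**4. Carry-over of a single 25% under-dose.** Assumptions: linear one-compartment kinetics, weekly dosing at steady state, trough sampling. The documents give no human half-life for EZN-2279. I used 72 to 300 h as an assumed range, with the dog values of 128 and 154 h (Section 5.3.1.2) inside it. Let r = 2^(−168/t½). The T-11 dose supplies a fraction r^(k−1)(1 − r) of the trough k weeks later, and the trough falls by 25% of that fraction. T-11 is Day 71 and T-15 is Day 99, so T-15 is k = 4.

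| t½ (h) | r | T-12 share → fall | T-13 share → fall | T-15 share → fall |
|---|---|---|---|---|
| 72 | 0.198 | 80.2% → 20% | 15.9% → 4.0% | 0.63% → 0.2% |
| 128 | 0.403 | 59.7% → 14.9% | 24.1% → 6.0% | 3.9% → 1.0% |
| 154 | 0.469 | 53.1% → 13.3% | 24.9% → 6.2% | 5.5% → 1.4% |
| 300 | 0.678 | 32.2% → 8.0% | 21.8% → 5.5% | 10.0% → 2.5% |

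No sample is taken at T-12. T-13 is sampled but is not a primary-endpoint week. Adding first-order absorption with a half-life of 12 to 48 h moves the T-15 figure by at most about 0.2 percentage points.

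**5. If the error spreads, which the text does not order.** For the same patient, the fall in the T-15 trough would be:
- T-11 and the dispensed T-12 dose both at 0.2 mg/kg: 25% × r²(1 − r²) = 0.9%, 3.4%, 4.3% and 6.2% at the four half-lives.
- T-11 through T-14 all at 0.2 mg/kg: 25% × (1 − r⁴) = 25.0%, 24.3%, 23.8% and 19.7%.

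**The case against.** The best defence is that the section corrects itself. The later sentence fixes when the injection is given and uses the same form as T-10 and T-13, so a site that follows it doses correctly. Section 10.7.2 is a second barrier, because an unagreed one-week change breaches both the agreement rule and the 4-week limit. Both points make literal execution less likely. Neither removes the conflict, since the protocol still orders two different doses at one visit.

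The second line is that no endpoint effect has been shown. This largely stands. The primary endpoint is erythrocyte dAXP, while the model gives only proportional changes in plasma ADA activity. It does not say whether any patient would cross either threshold. The full PK week (T-9) is over before T-11, and three further doses (T-12 to T-14) precede the T-15 sample.

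Third, the inputs are illustrative. The 40 U/kg figure is an example, not an enrolled patient's dose, and the 300 h limit has no source in the documents. The number of patients affected is unknown and could be zero. The spread scenarios in step 5 run against the later visit text, so they bound the consequence and do not predict it.

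Finally, dose administration and deviations are already to be recorded and listed. That is true, and it is why the remedy is small.

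**Conclusion.** The concern holds. Section 11.3.12 contains an unconditional fixed dose that contradicts the individual dose rule, every other treatment-period visit, and its own later sentence. Nothing in the SAP resolves it. It reads as a drafting error, not a deliberate choice.

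If followed literally, the protocol's 40 U/kg example patient is under-dosed by 25% for one injection, and a patient below 0.2 mg/kg is over-dosed. For the under-dosed patient the modelled effect on the T-15 ADA trough is 0.2% to 2.5% (1.0% to 1.4% at the dog half-lives). This rests on linear one-compartment kinetics at steady state and on an assumed human half-life. The primary endpoint would be at appreciable risk only if a site kept giving 0.2 mg/kg after T-11. The point should be fixed because it is an operative dosing instruction and the correction costs almost nothing.

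**What to change.** In Section 11.3.12, delete the words that specify 0.2 mg/kg, so that the patient receives his or her current individual dose, as at T-10, T-12 and T-13. Send sites a short notice. For patients already past Day 71, check the T-11 administration record and the T-12 dispensing and dosing records.

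Record any 0.2 mg/kg injection that differs from the patient's current dose as a deviation, using the listings already planned in SAP Sections 5.8 and 7.2. A with/without analysis is not needed unless the fixed dose turns out to have been carried forward towards T-15.

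The cost is one deleted phrase, one notice, and a check of two weeks of dosing records.
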